6.2.3 Safety Population

The Safety Population is defined as all participants who are randomized and receive at least one dose of study drug. The Safety Population will be used for all safety analyses, as well as demographic and baseline analyses.

6.3 Covariates and Subgroups

There are a limited number of covariates that will be incorporated in statistical models in our analyses because of the relatively small sample size in each treatment group: the baseline outcome measure. We will not impute missing values for baseline covariates.

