4.1 General Study Design and Plan

This study is a single-center, randomized placebo-controlled double-blind crossover study of VCN in participants with PD to assess its effects on measures of gait, balance, and cognition. Participants were randomized 1:1 to one of two treatment sequences: placebo followed by VCN 0.5 mg b.i.d., or

VCN followed by placebo. Participants received an initial 0.25 mg dose or equivalent placebo following baseline evaluations and were monitored for 4 hours after initial study medication administration with total daily dose or equivalent placebo escalated over the next 2 days. Treatment periods were 3 weeks in duration and interrupted by a 3-week washout period. Participants underwent a standard evaluation at baseline, at the end of the first treatment period (week 3 [day 22]), at end of the washout period-beginning of the second treatment period (week 6 [day43]), and at the end of the second treatment period (week 9 [day 64]).

The schema below describes the main elements of the study design:

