6.2.1 Intention to Treat Population

The main analysis set for efficacy is the intention to treat (ITT) population, defined as all participants randomized.

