7.3 Demographic and Baseline Variables

Demographic variables include: age at consent (defined as a continuous variable, e.g., 52.6 years), sex, race and ethnicity.

Baseline is defined as pre-treatment measures. Baseline variables include:

- Age at diagnosis (years)
- MDS-UPDRS III total score
- GDS score
- MoCA score

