8.1 Primary, Secondary and Exploratory Efficacy Analyses

For the Crossover study, linear mixed models containing treatment sequence, treatment period, treatment group, and dependent-variable baseline value, with participant within treatment sequence as a random effect, will be used for analysis of continuous outcomes. To compare differences between VCN and placebo, a test for carryover based on the sequence effect will be conducted using patient with sequence as the error term. Results will be presented as least squares (LS) mean and standard error (SE). The co-primary endpoints will be tested at the 2-sided, 0.025, significance level. All other tests will be based on a 2-sided significance level of 0.05; no adjustments will be made for additional multiple comparisons. Primary, secondary and key efficacy endpoints will be analyzed in all randomized participants (intention-to-treat [ITT] population) and in the Compliant Population.

Additional sensitivity analyses will be performed for UPDSR-III total and PIG subscale scores, where baseline degree of total cortical cholinergic denervation (from PET scans) and baseline degree of striatal dopamine denervation (from PET scans) were incorporated as covariates in separate models. These models will also be run for gait speed end points.

9 Safety Analyses

Safety endpoints will be analyzed in all randomized participants who received at least one dose of study medication (Safety Population). We will include adverse events that occurred in the washout period with the treatment given in period one.

Safety data, including adverse events (AEs) and the Columbia-Suicide Severity Rating Scale (C-SSRS), will be summarized descriptively by treatment group for the Safety Population.

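### Not imputing a missing baseline while adjusting for it removes participants who have both on-treatment values, at a modest and avoidable cost in precision

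*SAP*

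**What the plan says.** SAP 6.3 limits the model covariates to one, "because of the relatively small sample size in each treatment group: the baseline outcome measure", and then says "We will not impute missing values for baseline covariates". SAP 8.1 specifies "linear mixed models containing treatment sequence, treatment period, treatment group, and dependent-variable baseline value, with participant within treatment sequence as a random effect" for continuous outcomes, so the covariate enters the co-primary, secondary and exploratory analyses alike. SAP 6.2.1 says: "The main analysis set for efficacy is the intention to treat (ITT) population, defined as all participants randomized".

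SAP 7.3 says only "Baseline is defined as pre-treatment measures". SAP 4.1 names the baseline evaluation separately from the day-43 visit that ends washout, so day 0 is the natural reading, but no section says so outright.

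SAP 6.4 has a multiple-imputation fallback. It applies only if data are judged not missing at random, and it uses baseline as a predictor without a step to fill it in. No section says how a randomized participant with both outcomes and no baseline is handled.

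**The concern.** A mixed model cannot use a row whose covariate is missing. If a sway, gait or attention recording fails at day 0, both of that participant's rows leave the analysis of that endpoint, even when the day-22 and day-64 values are valid. In a two-period crossover the treatment comparison is made within participants, so a complete pair carries full information whether or not its baseline is known.

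Precision and power are at stake for both co-primaries, as is a consistent analysis set. SAP 3.2 lists more than 30 endpoints from separate instruments, so different people could drop out of different analyses for reasons unrelated to treatment.

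**Working it through.** **1. The plan's own figure.** Inputs are N = 33, at least 80% power, paired t-test, two-sided 0.025, and within-participant correlations of 0.64 (gait speed) and 0.72 (JERK), all from SAP 5. The rule of using the 95% upper bound of the SD is in the protocol, Specific Aim 2, Sample Size. The JERK SD is taken from protocol Table 3 (fallers, 0.125, n = 6).

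- Upper bound of the SD: 0.125 × √(5/χ²₀.₀₂₅,₅) = 0.307.
- SD of the difference: 0.307 × √(2 × (1 − 0.72)) = 0.229.
- With a difference of 0.131 and N = 33, noncentral-t power is 81.8%, and the smallest N reaching 80% is 32. The stated figure is reproduced.
- No SD is printed for gait speed. Exactly 80% at N = 33 implies a standardized within-participant difference of 0.559. That value is used below. It comes from N, power and alpha alone.

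**2. Why the covariate cancels.** Write the outcome of participant i in period j as

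y_ij = μ + sequence_i + period_j + τ·treatment_ij + β·b_i + u_i + e_ij.

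With one baseline b_i per participant,

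y_i2 − y_i1 = (period_2 − period_1) + τ·(treatment_i2 − treatment_i1) + (e_i2 − e_i1).

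The term β·b_i is gone. REML fits to three simulated trials (33 complete pairs; assumed SD 0.236, correlation 0.64, effect 0.112 m/s) agree. Each entry is estimate (SE):

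| Trial | No baseline | With baseline | Two pairs deleted | Two baselines mean-filled |
|---|---|---|---|---|
| 1 | 0.0884 (0.0325) | 0.0884 (0.0325) | 0.0833 (0.0341) | 0.0884 (0.0325) |
| 2 | 0.0917 (0.0379) | 0.0917 (0.0379) | 0.0822 (0.0396) | 0.0917 (0.0379) |
| 3 | 0.1394 (0.0352) | 0.1394 (0.0352) | 0.1243 (0.0358) | 0.1394 (0.0352) |

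**3. Where it does not cancel.**

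- *Incomplete pairs.* With 4 of 33 participants lacking period 2, adding the day-0 baseline moved the estimate by 0.004 m/s on average (largest 0.022 in 200 runs), because the model then uses between-participant information.
- *Period-specific baseline (day 0 and day 43).* The estimate moved even with complete pairs: 0.088 to 0.086, 0.092 to 0.121, and 0.139 to 0.153 in the same three trials.

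**4. Does mean-filling work with incomplete pairs?** Simulated trials had 37 participants, 4 lacking period 2 and 3 with baseline missing at random. The empirical SE was 0.0345 with all baselines, 0.0345 with mean-fill and 0.0358 with deletion, so deletion was about 4% worse (0.0358/0.0345 = 1.038). There was no material bias under any of the three.

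**5. Size.** The protocol enrolls 42 and allows 10% attrition: 42 × 0.90 = 37.8, so about 37 completers. Power uses the noncentral t with standardized difference 0.559, two-sided 0.025 and N − 2 degrees of freedom (period in the model). The SE ratio is √(N/(N − k)) for k pairs lost.

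| Pairs lost | From 37: power | SE rise | From 33: power | SE rise |
|---|---|---|---|---|
| 0 | 85.0% | – | 79.9% | – |
| 1 | 83.8% | 1.4% | 78.4% | 1.6% |
| 2 | 82.6% | 2.8% | 76.9% | 3.2% |
| 3 | 81.3% | 4.3% | 75.2% | 4.9% |
| 4 | 79.9% | 5.9% | 73.5% | 6.7% |

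JERK has more margin. On the N − 1 basis of step 1, power is 81.8% at 33 pairs, 80.4% after one loss and 78.9% after two. The number of missing baselines is an assumption throughout.

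**The case against.** The strongest reply is that this may never happen. SAP 4.1 has the first dose follow the baseline evaluations, and no section reports or predicts a missing baseline. That stands as a limit on size. It does not supply the missing rule, since a single failed recording is enough to trigger the problem for one endpoint.

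Four stronger readings are tempting, and the documents do not support them.

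- *The covariate can never change the estimate.* This is true only for complete pairs and a single day-0 baseline. The plan allows for attrition, its missing-at-random mixed model can keep incomplete pairs, and SAP 7.3 does not rule out a period-specific baseline.
- *The SAP orders these participants to be excluded.* It does not. Exclusion follows from how the specified model treats a missing covariate. Fitting without the covariate would also comply with SAP 6.3.
- *The rule flatly contradicts intention to treat.* SAP 6.2.1 defines a set, "defined as all participants randomized". Participants with no on-treatment value contribute nothing to the model under any rule. The real tension is narrower: people with usable outcomes are lost.
- *Power falls to 73.5%.* That counts four losses down from exactly 33 pairs, whereas planned enrollment leaves about 37.

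The shifts in step 2 after deleting two pairs are also not evidence of bias. They show the sampling effect of removing two people from one dataset.

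**Conclusion.** The point holds as a modest, avoidable loss. SAP 6.3 and 8.1 together remove a participant with both on-treatment values and no day-0 recording from an analysis described as all randomized, and the fallback in SAP 6.4 does not bring that participant back. For complete pairs with a day-0 baseline nothing is gained in return. For incomplete pairs baseline matters slightly, and mean-filling preserves what it offers.

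The size is about 1.5% in SE and 1.2 to 1.5 power points per lost pair. At about 37 completers it takes four losses to reach 79.9%. With completers near 33, one loss puts gait speed at 78.4%, and two put JERK below 80%. This rests on an assumed number of missing baselines, on gait-speed variability back-solved from the stated power, and on baseline meaning the day-0 value.

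**What to change.** Replace the no-imputation sentence in SAP 6.3 with: *Baseline is the day-0 pre-treatment value; a missing baseline is set to the mean of the observed day-0 values pooled over both sequences, so that every randomized participant with at least one on-treatment value enters the model.*

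The filled value ignores sequence and treatment, so it can be fixed before unblinding. The definition of baseline has to come with it, because the fill has no clear meaning if baseline could be period-specific. The cost is one SAP sentence and one line of code. Omitting the covariate for an affected endpoint would also keep complete pairs, but it gives up the small contribution of baseline when pairs are incomplete. Reporting the number of filled baselines per endpoint would show whether the rule mattered.

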6.4 Missing Data

We will summarize the extent of missing data over time for the primary end points. We will

investigate the missing data mechanism (missing at random, not missing at random), which is important for the validity of our analytic approaches, through exploratory analysis. Exploratory analyses will include plots of the mean profile of end points at weeks 0, 3, 6, and 9 by treatment sequence for those who have complete data throughout the study and those who don't.

The primary analysis of the primary end points assumes a missing at random mechanism. If data are not missing at random, we will use a multiple imputation approach within the pattern-mixture model framework [8]. The imputation models, applied sequentially for each missing data pattern, will include baseline value, treatment group, and demographic variables (age and gender), allowing for the dependence of later time points on earlier time points. If there are issues with over-fitting, the demographic variables will be omitted. The analysis model will include the same covariates used in the primary analysis of the primary end points and will incorporate the uncertainty due to imputation in the calculation of the standard error, as described by Rubin [9].

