Analysis Method. For all aims, we will conduct exploratory analyses to examine the distributions of outcomes under each treatment, as well as individual and mean profiles over time. Graphical approaches such as boxplots and scatterplots with linear or non-linear (e.g., loess) methods will be used, allowing identification of outliers, linearity, and correlation of measurements within person and across time. If outcome data do not appear normally distributed, transformations will be employed. Because participants' outcomes will measured at more than one time point per person, our analyses will be based on linear mixed effects models (108-110). We expect no carryover since treatments will be spaced three weeks apart. Tests to compare treatments will be based on Wald and chi-squared tests based on maximum likelihood or restricted maximum likelihood methods. Alternative covariance structures (other than compound symmetry) will also be explored and model fit examined using the Akaike Information Criteria (AIC).

Potential Problems and Alternatives: All measures proposed for this experiment are well established in the University of Michigan Functional Neuroimaging, Cognitive and Mobility Laboratory and the **Clinical Resource Core**. The major foreseeable difficulties are subject recruitment and retention. We've had considerable success recruiting and retaining subjects in protocols involving up to 4 PET studies, serial evaluations, long-term follow-up (months to years), and subject clinical-psychometric-gait & balance evaluations as intensive as those proposed. We budget a 10% drop out rate in this study, which is typical of our experience in prior prospective studies and identical to the dropout rate in the recent AD study (89). A related concern would be unexpected difficulty with VCN tolerability, leading to excessive dropouts. The goal of the SA1 experiments is to find the lowest dose providing high  $\alpha 4\beta 2^*$  nAChR occupancy, which provides protection against this possibility. In the recent AD study, VCN was tolerated well at higher doses than we expect to employ. If tolerability is a problem, we would use a slower dose escalation regimen.

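### SAP 6.4 makes its only not-missing-at-random analysis depend on a finding that observed data cannot supply, and states no identifying restriction or delta

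*SAP*

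**What the plan says.** SAP 6.4 sets out four steps.

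- **Diagnosis.** The team will "investigate the missing data mechanism (missing at random, not missing at random") through exploratory analysis. "Exploratory analyses will include plots of the mean profile of end points at weeks 0, 3, 6, and 9 by treatment sequence", contrasting participants who have complete data with those who do not.
- **Primary assumption.** "The primary analysis of the primary end points assumes a missing at random mechanism".
- **Fallback.** "If data are not missing at random, we will use a multiple imputation approach within the pattern-mixture model framework".
- **Form of the fallback.** "The imputation models, applied sequentially for each missing data pattern, will include baseline value, treatment group, and demographic variables" (age and gender), with later time points allowed to depend on earlier ones. "If there are issues with over-fitting, the demographic variables will be omitted". The analysis model keeps the primary covariates, and standard errors allow for the imputation.

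No criterion is given for concluding that data are not missing at random. No identifying restriction, delta or tipping-point range is stated.

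Elsewhere, SAP 6.2.1 makes all randomised participants the main efficacy set, and SAP 8.1 analyses them with a linear mixed model. SAP 3.2 places the efficacy endpoints at days 22 and 64. The protocol (Specific Aim 2, Sample Size) enrols 42. Its Potential Problems paragraph says "We budget a 10% drop out rate in this study".

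**The concern.** Missing at random and not missing at random differ only in how the unobserved values are distributed, given what was observed. No plot or test of observed data bears on that difference. If non-completers look different at baseline or at week 3, this is evidence against missing completely at random, and it is fully compatible with missing at random. The condition in SAP 6.4 therefore has no answer in the data.

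Without a criterion, whether the sensitivity analysis appears is decided after the data have been seen. The plots are split by treatment sequence, SAP 6.1 places the final analysis after unblinding, and no masked review of the mechanism is described.

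The protocol foresees drug-related dropout. Its Gastrointestinal Symptoms paragraph (Protection Against Risk) withdraws participants who still cannot tolerate varenicline after dose reduction, and the Specific Aim 2 Potential Problems paragraph names tolerability as a possible cause of excessive dropout. Losses of that kind are where a reader would want the missing-at-random assumption tested.

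**Working it through.** **1. Does another planned analysis test the assumption?** The Compliant Population (SAP 6.2.2, 8.1) removes participants. The models with PET covariates (SAP 8.1) add predictors. Neither changes what is assumed about missing outcomes. The protocol's Analysis Method paragraph has no missing-data sensitivity analysis.

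**2. How many dropouts?** Inputs are 42 enrolled, 10% attrition and 33 evaluable (protocol, Sample Size; SAP 5).
- Stated rate: 42 × 0.10 = 4.2 expected, with a 95% binomial range of 1 to 8.
- The plan's 42 is not reproduced: 33/0.90 = 36.7, or 37. Enrolling 42 leaves room for 9 losses (1 − 33/42 = 21.4%). This is a separate matter and serves here only as an upper case.

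**3. What could the plots show?** Take a true baseline gap of 0.5 SD (an assumption) between non-completers and completers, tested two-sided at 0.05. Power is 15% for 4 versus 38 and 25% for 9 versus 33. A detected gap would still count only against missing completely at random.

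**4. Which patterns matter?** With outcomes at days 22 and 64 there are two monotone patterns: both missing, or day 22 observed and day 64 missing. In either, the missing values are by definition absent from that pattern's own data. They must be borrowed from other participants under a stated restriction, or shifted by a stated delta.

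**5. Size, simple calculation.** A paired t-test with n = 33, two-sided alpha 0.025 and 80% power needs a standardised difference of 0.559 SD of the paired difference. Suppose 4 of 42 have no benefit:
- All-randomised effect: (38 × 0.559 + 4 × 0)/42 = 0.506 SD.
- Movement: 4/42 × 0.559 = 0.053 SD, or 9.5% of the completer effect.
- Standard error with 38 pairs: 1/√38 = 0.162 SD. Ratio: 0.053/0.162 = 0.33.

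**6. Size, imputation calculation.** Assumptions: gait effect 0.112 m/s, SD of the difference about 0.20 m/s (implied by 0.112/0.559, not stated in the documents), correlation 0.64, N = 42, and 10% missing the day-64 visit only. Missing values were predicted from a regression in completers on baseline, day 22 and sequence, and delta was added where the missing visit was a varenicline visit. The regression was full rank in all 4,000 simulated trials.

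| Delta (m/s) | Mean estimate (m/s) |
|---|---|
| 0 | 0.112 |
| −0.112 | 0.106 |
| −0.224 | 0.101 |

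Check: half the dropouts miss a varenicline visit, so the shift is ½ × 0.10 × 0.112 = 0.0056 m/s, or 5%. Against a standard error of 0.20/√42 = 0.031 m/s, that is 0.18. The simulation shows estimability and the size of the shift. It used a single regression imputation, so it says nothing about multiple-imputation standard errors.

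**7. Upper case.** With 9 of 42 lost, step 5 gives 9/42 × 0.559 = 0.120 SD. Against 1/√33 = 0.174 SD, the ratio is 0.69.

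**The case against.** The best defence is that this is a pilot target-engagement study with few expected dropouts, an openly stated assumption and a named fallback. The exploratory work is not limited to plots, and the extent of missing data and the reasons for dropout (SAP 7.1) are also reported. Investigators could use these to make a reasoned decision to run the fallback. The protocol reports good tolerability at higher doses in an Alzheimer's disease trial, so drug-related dropout is foreseen but not shown to be likely. The mixed model keeps day-22 data from later dropouts, so the completer arithmetic in step 5 does not describe the planned analysis. All of this stands, and it limits the size of the problem. It does not make the condition answerable.

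Four stronger readings are tempting, and the documents do not support them.
- **That the pattern models cannot be fitted.** SAP 6.4 applies models for each pattern but does not confine estimation to that pattern's own data. Step 6 shows that borrowing from completers works at this sample size. The defect is a missing specification.
- **That the fallback can never run.** It can be invoked by judgement. What the data cannot do is justify it.
- **That about 4 dropouts are spread over three patterns.** Weeks 3, 6 and 9 are the disposition time points in SAP 7.1; the analysed endpoints give two.
- **That sequence and period are missing from the imputation.** In a visit-by-visit model of a two-sequence, two-period crossover, the visit fixes the period and treatment at that visit fixes the sequence. It would help to say that treatment group means treatment at the visit.

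**Conclusion.** The concern holds as a fault in a stated rule: the only check on missing at random depends on a finding that cannot be made from observed data, and its content is left open. The effect on the estimate is modest. At the stated attrition, and if the missing participants had no benefit, it is about 5% (imputation calculation) to 10% (completer calculation), or 0.18 to 0.33 of a standard error. This assumes the design effect is true and about 4 of 42 are lost. At 9 losses the completer calculation roughly doubles the movement, to about 0.7 of a standard error. Shifts of that order matter mainly if a co-primary result lies near the 0.025 threshold. The change should be made because it is cheap and removes a choice that depends on the data, not because the primary result is expected to be wrong.

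**What to change.** In SAP 6.4, delete the condition and pre-specify the following sensitivity analysis for both co-primary endpoints, to be reported whatever the exploratory plots show.

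1. Multiply impute each missing visit from participants with that visit observed, pooling patterns. Use visit-specific models with baseline, earlier outcomes and the treatment received at that visit.
2. Shift the imputed varenicline-period values over a stated grid of deltas, from zero to at least the full design effect, towards no benefit or harm (downwards for gait speed, upwards for JERK). The full effect is 0.131 m²/s⁵ for JERK. For gait speed the protocol gives 0.112 m/s and the SAP 0.122 m/s; reconcile these before fixing the grid.
3. Analyse each completed data set with the SAP 8.1 model, combine the results as SAP 6.4 already describes, and report the delta at which the conclusion at two-sided 0.025 changes.

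Keep the profile plots as description, without a decision attached. The primary mixed model, sample size and trial conduct do not change. The cost is a paragraph of SAP text and a little programming.
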